#### 6.1.1 Treatment regimens / study intervals

The treatment setup in the O\*C database will contain the following study intervals: screening (starting with the date of informed consent at 0:00 h), run-in (starting with the date of run-in medication, time 0:00 h), linagliptin and glimepiride (each of the treatments starting with the date and time of first drug administration), off-treatment (starting with any date and time of last drug administration + 1 day, time 0:00 h, if the study drug is re-started afterwards), post-treatment (starting with the last date and time of last drug administration + 1 day, time 0:00 h), and post-study (starting with the date of trial completion + 1 day, time 0:00 h).

During the study treatment phase, patients are allowed to go off study drug and subsequently re-start study drug. This may happen not at all or repeatedly for a given patient, as this study is expected to go on for a number of years. This is reflected by the off-treatment phase. Further, a patient might die or discontinue from the study.

If the date of last drug administration is identical to the date of trial completion, post-treatment starts with the date of trial completion + 1 day and post-study period starts with the date of trial completion + 2 days, both at time 0:00 h.

For specific safety and efficacy parameters the duration of the on-treatment phase is given in [Section 6.7.2](#).

For detailed information on the handling of the treatment in the O\*C views and the definition of analysis treatments refer to Technical TSAP ADS plan.

A summary table will display the actual dose of glimepiride at the different visits, including the number of patients on each dose and the mean, SD, median and mode of dose per visit. However, none of the treatment comparisons will take into account the actual doses of glimepiride, only the treatment groups 'glimepiride' and 'linagliptin' will be displayed.

Patients will be analysed as randomised for all analyses (safety and efficacy).

If the Interactive Voice and Web-based Response System (IXRS)-assigned study medication is not available at the site, a forced randomisation will occur, and the IXRS will assign a

treatment that is available at the site. Also, if a site assigns treatment to a patient before calling the IXRS, this is considered a forced randomisation. In both cases, that patient will receive the same treatment for the remainder of the trial.

(If a patient erroneously receives the wrong trial drug, patients are asked to return to the site and dispensed correct drug as soon as possible.)

## **6.2 IMPORTANT PROTOCOL VIOLATIONS**

Data discrepancies and deviations from the CTP will be identified for all patients randomised and/or treated.

A protocol violation (PV) is important, if it affects the rights or safety of the study patients or if it can potentially influence the primary and/or key secondary outcome measures for the respective patients in a way that is neither negligible nor in accordance with the study objectives.

This second category of important PV forms the basis for the decision of whether a patient belongs to an analysis set.

The following table contains the categories which are considered to be important protocol violations in this trial. If the data show other important PVs, this table will be supplemented accordingly, latest at the BRPM.

The important PVs will be described in the CTR. A listing of patients with medication code broken will be provided, although this is not defined as IPV.

Table 6.2: 1 Important Protocol Violations

Category / Code	Description	Comment/Example	Affects rights or safety (R/S) or primary/ key secondary outcome (E)	Excluded from
A	Entrance Criteria Not Met			
	Inclusion criteria violated			
A1.1	No type 2 diabetes	Inclusion criterion IN1 ticked „No“	E	PPS
	Exclusion criteria violated			
A2.1	Type I diabetes	Exclusion criterion EX1 ticked „Yes“	E	PPS
A2.4	Preplanned planned coronary artery re-vascularization (PCI, CABG)	Exclusion criterion EX7 ticked „Yes“	E	PPS
A2.7	Congestive heart failure of NYHA class III or IV	Exclusion criterion EX10 ticked „Yes“	E	PPS
A2.8	Specific exclusion criterion for premenopausal women violated	Exclusion criterion EX17 ticked „Yes“	R/S	None
A2.9	Patient considered unreliable by the investigator for safe participation in the study	Exclusion criterion EX18 ticked „Yes“	E	PPS

Table 6.2: 1 (cont'd.) Important Protocol Violations

Category / Code	Description	Comment/Example	Affects rights or safety (R/S) or primary/ key secondary outcome (E)	Excluded from
B	Informed Consent			
B1	Informed consent not available	Inclusion criterion IN6 ticked „No“ or Date of informed consent missing or No signature on patient's "Declaration of Informed Consent" (to be identified by CRA)	E, R/S	TS, OS, PPS, Screened patients
B2	Informed consent given too late	Date of informed consent for the study not obtained prior to any study related procedure. Minimum requirement for initial informed consent <= date of Visit 1a/date of any study procedure	R/S	None
C	Trial medication and randomisation			
C1	Incorrect Trial Medication Taken			
C1.1	No study medication taken	Patient randomised, but no study medication taken.	E	TS, OS, PPS

Table 6.2: 1 (cont'd.) Important Protocol Violations

Category / Code	Description	Comment/Example	Affects rights or safety (R/S) or primary/ key secondary outcome (E)	Excluded from
C1.2	Incorrect trial medication taken	Wrong medication (different medication than the patient was randomised to) taken for more than 20% of the overall treatment duration of a patient. This is identified by the medication kit number recorded in eCRF as well as the medication kit number as assigned by IXRS. Can also be manually identified by investigator or CRA. Can only be finally judged after DBL since unblinding information is required.	E	PPS
C2	Randomisation not followed			
C2.1	Treated before calling IXRS	Date of randomisation call after date of study drug intake at visit 2	E	PPS
C3	Non-compliance			
C3.2	Non-compliance with criteria for removal from study medication	This includes only the following case: although a patient is pregnant, she is treated. A missing pregnancy test does not qualify as IPV.	R/S	None

Table 6.2: 1 (cont'd.) Important Protocol Violations

Category / Code	Description	Comment/Example	Affects rights or safety (R/S) or primary/ key secondary outcome (E)	Excluded from	
D	Concomitant Medication				
D1	Improper medication washout				
	D1.1	Glinide or SU not stopped until 35 days after first study drug intake	For patients on SU/glinide at baseline: Date of termination of glinide or SU > Date of first trial drug intake + 35 days	E	PPS
D2	Prohibited medication use during the treatment period of the trial	Not applicable.			
D3	Mandatory medication not taken	Not applicable.			
E	Missing data	Not applicable.			
F	Incorrect timing	Not applicable.			
G	Trial specific protocol violations				
	G1.1	Previous participation within this study		E, R/S	PPS
	G1.2	Serious non-compliance potentially affecting primary endpoint*		E, R/S	PPS*

**Note:** Missing visits, evaluations, and tests will be considered missing data, not protocol deviations.

\*These patients might be kept out of some further patient analysis sets. The details are described in a separate document.

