## 4.2.2 Restrictions

### 4.2.2.1 Restrictions regarding concomitant treatment

The use of other antidiabetic agents (next to background therapy and any rescue therapy) such as other oral agents, short-acting insulin\* or injectable GLP-1 analogue/agonists will be prohibited during the course of the study.

\*Short acting insulin may be given as rescue medication for up to two weeks (e.g. during hospitalisation).

Additionally treatment with anti-obesity drugs is prohibited.

In case metformin is used as background therapy and participants are in need for intravascular administration of iodine containing contrast agents: metformin is allowed to be discontinued according to local practice; usually before administration and 48 hours afterwards.

If any restricted treatments or any other concomitant drugs interfering with the study medication are given during the conduct of the trial, the study medication dose can be reduced, or the study medication can be discontinued temporarily, or if needed permanently (see also Section [3.3.4.1](#)).

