**Proprietary confidential information.**

© 2019 Boehringer Ingelheim International GmbH or one or more of its affiliated companies. All rights reserved.

This document may not - in full or in part - be passed on, reproduced, published or otherwise used without prior written permission.

- Randomised study drug: incorrect active study drug taken.
- Severe violation of treatment compliance (defined as less than 50% of visits from Visit 3 on (excluding placebo run-in phase) with treatment compliance outside 80-120% range.
- Non-adherence to other specifications of the protocol that could bias the primary endpoint

Additionally 30-days-treatment set of patients will be created for sensitivity analysis. The 30-days-treatment set will include all randomised patients with a minimum treatment duration of 30 days.

All patients treated with at least one dose of study drug (the Treated Set) will be included in the safety evaluation.

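### No listed per-protocol criterion or censoring rule covers a prohibited SU, glinide or DPP-4 inhibitor newly started alongside study drug or during an interruption

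*SAP*

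**What the plan says.** **The prohibition.** Protocol 4.2.2.1 prohibits the following during the study: "The use of other antidiabetic agents (next to background therapy and any rescue therapy) such as other oral agents", short-acting insulin (with a two-week exception) and injectable GLP-1 agents. SUs, glinides and DPP-4 inhibitors are not named there; they fall under other oral agents. The rescue options in protocol 4.2.1 (pioglitazone, metformin, alpha-glucosidase inhibitor, basal insulin) include none of them.

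**What follows if it is breached.** Protocol 4.2.2.1 says that "the study medication dose can be reduced, or the study medication can be discontinued temporarily, or if needed permanently". For rescue outside the protocol list, protocol 4.2.1 asks for study drug to stop only where the combination is contraindicated. A patient can therefore be on both.

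**The per-protocol set.** Protocol 7.3 lists among important violations "Non-adherence to other specifications of the protocol that could bias the primary endpoint". SAP Table 6.2: 1 marks row D2, "Prohibited medication use during the treatment period of the trial", not applicable, with no outcome flag and no excluded set. The same table excludes from the PPS:
- C1.2: "Wrong medication (different medication than the patient was randomised to) taken for more than 20% of the overall treatment duration of a patient"
- D1.1: "Glinide or SU not stopped until 35 days after first study drug intake", limited by its comment: "For patients on SU/glinide at baseline: Date of termination of glinide or SU > Date of first trial drug intake + 35 days"

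**Censoring.** The primary analysis is ITT on the treated set, with censoring independent of study drug intake (SAP 6.8.3, 7.4.1). The supportive runs (TS+0, TS+7, TS+30, and PPS and OS at 30 days) end follow-up a fixed number of days after the last study drug intake, or at trial completion if that is earlier (SAP 6.8.3, 7.4.2.2).

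**The concern.** The trial compares two drugs for non-inferiority. When a linagliptin patient takes an SU, or a glimepiride patient takes a DPP-4 inhibitor, the arms become more alike and any true difference shrinks. The ITT analysis accepts this by design. The PPS and on-treatment runs are where a reader would look to see whether the ITT result depends on it, and for one kind of use they cannot show it.

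The table also treats similar exposures differently. A baseline SU kept beyond 35 days is flagged as affecting outcome and leads to PPS exclusion. An SU newly started on day 36 and taken for years leads to nothing, although the treatment period is estimated at up to 432 weeks.

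**Working it through.** **1. Which use do the listed rules reach?**

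| Use of an SU, glinide or DPP-4 inhibitor | PPS | TS+0, TS+7, TS+30, OS |
|---|---|---|
| Baseline SU or glinide kept beyond 35 days | Excluded (D1.1) | No rule |
| Started after permanent stop of study drug | Cut at 30 days | Cut at 0, 7 or 30 days |
| Newly started while study drug continues | No rule | No rule |
| Started during an interruption, study drug later resumed | No rule | No rule |

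The last row follows from two provisions. Protocol 3.3.4.1 sets no limit on the number or length of interruptions and allows a new antidiabetic regimen once study drug is stopped. The censoring date in SAP 6.8.3 and 7.4.2.2 is tied to the last stop only. Time on the other drug during an interruption therefore counts as on-treatment even in TS+0.

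The overview of primary-endpoint analyses (SAP Table 7.4.2.2: 1) shows no further run. SAP 5.3, 6.4 and 7.4.3 are not in the public text, so an analysis described there cannot be excluded.

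**2. The plan's own figures.** Inputs from protocol 7.3.1 and 7.6: 631 events, margin 1.3, one-sided 2.5%, 1:1 allocation.
- SE(log HR) = 2/√631 = 0.0796.
- Non-inferiority power at HR 1.0: Φ(ln 1.3/0.0796 − 1.96) = 90.9%, as stated.
- Superiority power at HR 0.8: 80.0%, as stated.

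**3. Illustration of dilution at the margin.** Non-inferiority is declared if the estimated log HR is below ln 1.3 − 1.96 × 0.0796 = 0.1063. Assume a true HR of 1.3 and that a share c of person-time takes the other arm's hazard. The documents give no value for c.
- One-way (linagliptin patients only): HR = 1.3(1 − c) + c.
- Two-way: HR = [1.3(1 − c) + c] / [(1 − c) + 1.3c].
- P(declare non-inferiority) = Φ((0.1063 − ln HR)/0.0796).

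| c | Expected HR | False non-inferiority |
|---|---|---|
| 0 | 1.300 | 2.5% |
| 5%, one-way | 1.285 | 3.5% |
| 10%, one-way | 1.270 | 4.8% |
| 20%, one-way | 1.240 | 8.6% |
| 10%, two-way | 1.233 | 9.8% |

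A second model, which shrinks the log HR by 5%, 10% or 20%, gives 3.6%, 5.2% and 9.7%.

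**4. Direction.** Dilution moves the HR towards 1 from either side. At a true HR of 1.0, non-inferiority power stays at 90.9%. At 0.8, shrinking the log HR by 10% gives an HR of 0.818 and cuts superiority power from 80.0% to 71.3%.

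All figures use the nominal 2.5%. The final level after the interim analyses and the Bonferroni step is slightly lower and is not stated as a number.

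**The case against.** **The list is not closed.** SAP 6.2 adds: "If the data show other important PVs, this table will be supplemented accordingly, latest at the BRPM". That is a blinded meeting, and protocol 7.3 has its catch-all. A criterion could therefore still be added. But adding one is left to judgement on the accumulated data, while the pre-specified entry for a known prohibition is not applicable. The clause makes the fix easy; it does not make it unnecessary.

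**Some of this use is already handled.** A reader might infer that no planned analysis removes anyone on an open-label SU or DPP-4 inhibitor. The documents do not support that. D1.1 removes continued baseline SU or glinide from the PPS, and every on-treatment run cuts follow-up soon after permanent stop. The gap is the last two rows of the first table.

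**The arithmetic prices switching.** This stands. A linagliptin patient who adds an SU still takes linagliptin, and nothing in the documents says that the hazard then equals that of the glimepiride arm. C1.2 concerns replacement of the assigned drug, so it is only a loose comparison for add-on use.

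**The direction depends on the truth.** This also stands. A reader might infer that crossover always favours the sponsor's claim. It favours a false non-inferiority claim only if the true HR is above 1. That is the case that matters for type I error, which is defined at 1.3.

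**Conclusion.** The gap is real and narrow: a prohibited SU, glinide or DPP-4 inhibitor newly started alongside study drug, or during an interruption, stays in every listed run. This does not fit protocol 4.2.2.1, protocol 7.3 or the SAP's own row D1.1.

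Its size is unknown because no usage rate is given. The range of 3.5% to 8.6% for one-way use rests on assumed shares of 5% to 20%, a true HR of 1.3, 631 events and full adoption of the other arm's hazard. It should not be read as the trial's error rate, nor as something that the change below would repair. It describes the primary test, which stays as planned, and the supportive runs will have fewer events. What the gap costs is the value of those runs as a check: if the true HR is above 1, they carry some of the same dilution as the ITT estimate that they are meant to probe.

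Closing it is a cheap improvement.

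**What to change.** Before unblinding, with the primary ITT analysis unchanged:

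1. Add one supportive TS+30 run that also censors at first intake of an open-label SU, glinide or DPP-4 inhibitor plus 30 days, if that comes earlier. Apply it to both arms alike, so that it can be derived blind.
2. Replace the D2 entry with a pre-specified criterion (category E, PPS) for such use beyond a stated duration. Censoring PPS follow-up at first such use is preferable to excluding the whole patient on cumulative exposure, because a patient must stay in follow-up long enough to accumulate it, so exclusion would select on follow-up time. The 35 days in D1.1 should not be carried over without thought. SAP Section 4 derives it as a washout tolerance (day 28 visit plus 7 days), and it is about 1.2% of 432 weeks (35/3024 days), against the 20% in C1.2.
3. Report the frequency of such use by arm, separating use alongside study drug from use during interruptions.

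**Cost.** SAP wording, one extra run and one table. Concomitant and rescue medication is already recorded in the eCRF (protocol 4.2.1), and SAP 7.2 already tabulates antidiabetic therapies started after first intake. The censoring may be informative, and applying the rule to both arms also drops same-class use that is not crossover. The runs will have fewer events and should remain sensitivity analyses.

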### **6.3 PATIENT SETS ANALYSED**

- **Treated set (TS):**  
All patients treated with at least one dose of study drug. The TS is the basis for all efficacy and safety analyses.
- **Per protocol set (PPS):**  
Patients included in the TS who have important protocol violations will be excluded from the PPS. A protocol violation will be considered important if it can be expected to have a distorting influence on the assessment of the primary endpoint and/or key secondary endpoints.
- **On-treatment set (OS):**  
The 30-days-treatment set will include all randomised patients with a minimum treatment duration of 30 days. It is used for sensitivity analysis.  
The time from last permanent treatment stop (excluding reported treatment gaps) minus first drug intake + 1 day has to be equal or greater than 30 days to qualify a patient to be included in this analysis set.

The following table defines for each planned analysis, which patient set is to be used.

Table 6.3: 1 Patient sets for analyses

Endpoint	TS	Patient set	
		PPS	OS
Primary/Key secondary endpoints	X	X*	X*
Occurrence of 4P-MACE, 3P-MACE	X	X*	X*
Occurrence of and time to the first occurrence of composite endpoint of all CEC confirmed adjudicated events/ Tertiary CV endpoints/ non-CV death	X		
Secondary/Tertiary diabetes related endpoints	X		
Adverse events, safety laboratory, vital signs, hypoglycaemia related endpoints	X		
Other endpoints not mentioned above (excluding adverse events, safety laboratory, vital signs, hypoglycaemia related endpoints, non-CV death)	X		
Demographic/baseline characteristics	X		
Important PVs	X		

Disposition is based on enrolled (defined as patients with signed informed consent), randomised and treated patients. Patient analysis sets are displayed on all randomised patients.

\* Sensitivity analysis

Note that the number of patients with available data for an endpoint may differ. For details, see section “Handling of missing data”.

### 6.3.1 Serious non-compliance potentially affecting primary endpoint

If an individual site is closed for serious non-compliance (SNC), any decisions regarding the use of the data will be made as detailed in (6) before unblinding and documented separately.

Further, any decisions with respect to inclusion/exclusion from the PPS will be documented separately.

The analysis of data from patients who participated at more than one investigator site in this study will be described in a separate document.

## **6.5 POOLING OF CENTRES**

As stated in the CTP, no centre effect is included into the model, as the centre size is usually expected to be rather small.

Furthermore, due to the anticipated low event rate a sufficient number of events per centre for the analysis of a centre effect and a centre by treatment interaction are not expected.

A pooling of centres is not planned; primary and key secondary endpoints will be explored by geographical region only.

## **6.6 HANDLING OF MISSING DATA AND OUTLIERS**

Every effort will be made to collect data as complete as possible. Missing data will be handled as outlined below.

For time to event analysis, patients who do not have a specific event will be censored (for details, refer to [Section 6.8](#)).

Different methods will be used to handle missing data for diabetes related endpoints of this trial. The following paragraphs outline the general approach. Refer to [Table 6.6: 1](#) below for more details.

### Observed cases (OC)

Only the available data that were observed while patients were on study medication (defined as time from first drug intake until last permanent treatment stop date plus the endpoint specific follow-up time) will be considered. Missing data will not be replaced. Any values taken after rescue medication intake will be set to missing.

### Observed cases – Rescue observed cases (OC-ROC)

Only the available data that were observed while patients were on study medication (defined as time from first drug intake until last permanent treatment stop date plus the endpoint specific follow-up time) will be considered. Missing data will not be replaced. Any values taken after rescue medication intake will be kept.

### Observed cases - ALL (OC-ALL)

All available data will be considered, including values obtained on treatment and post-treatment. Missing data will not be replaced. Any values taken after rescue medication intake will be kept.

### Last observation carried forward (LOCF)

Any values taken after rescue medication intake will be set to missing. The last observed on-treatment value (within the time window from first drug intake until last permanent treatment stop date plus the endpoint specific follow-up time) will be carried forward, whether or not it is selected/picked as the value for the respective previous week (if multiple measurements were performed within a time window for a visit, as described in [Section 6.7.3](#)). That means, for patients receiving rescue therapy the last on-treatment measurement prior to the intake of rescue therapy will be carried forward. Missing values before baseline will not be imputed.

One missing value within a course of measurements on treatment will be interpolated based on the last observed value before the missing visit and the first observed value after the missing visit.

(This is independent from the selection of a value as the picked visit value to be used in the descriptive analysis by week, as described in [Section 6.7.3](#)).

Interpolation will be done according to the formula described below. Let:

$D_0$  = date of a visit with a missing value for an endpoint;

$D_1$  = date of the next visit, with endpoint value non-missing, after the visit with missing value;

$D_{-1}$  = date of the previous visit, with endpoint value non-missing, before the visit with missing value;

$E_i$  = endpoint values for visits  $D_{-1}$ ,  $D_0$ ,  $D_1$  for  $i = -1, 0$  and  $1$ .

Then the missing value will be interpolated as:

$$E_0 = E_{-1} + \left( (E_1 - E_{-1}) \times \frac{D_0 - D_{-1}}{D_1 - D_{-1}} \right)$$

Replacement of missing values will be performed for all weeks up to the last planned week that could have been reached by a patient, based on individual randomisation into the trial. Refer to [Section 7.5.1](#) for the definition of this planned final visit.

In general baseline results will not be carried forward in case of missing on-treatment values, but can be used for interpolation.

Only, if a patient receives rescue therapy before the first available on-treatment HbA1c measurement, the HbA1c baseline value will be carried forward.

For all other parameters, except HbA1c, no baseline values will be used to replace post rescue measurements.

All values documented after last permanent study treatment stop will be set to missing for the analysis; instead, values derived by on-treatment LOCF will be analysed. That means, post-treatment values following the last permanent study treatment stop will not be considered, not even for interpolation.

